9.2.1.4 Outcome Assessment

Investigators will be instructed to report to the Sponsor or its designee their assessment of the outcome of each AE (both serious and non-serious). Definitions for possible AE outcomes include:

- Recovered/Resolved: the event has improved or the patient recuperated
- Recovered/Resolved with Sequelae: the patient recuperated but retained pathological conditions directly resulting from the disease or injury
- Recovering/Resolving: the event is improving
- Not Recovered/Not Resolved: the event has not improved or the patient has not recuperated
- Fatal: termination of life as a result of an AE. There should be only one AE marked with this outcome
- Unknown: not known, not observed, not recorded, or refused

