9.1.3 Serum Chemistry, Hematology, and Urinalysis

Serum chemistry, hematology, and urinalysis will be performed at the times specified in Table 4, Table 5, and Table 6. In particular, safety laboratory assessments will be performed daily for the first 7 days post-gene therapy infusion (see Section 8.1.3).

Serum chemistry includes aspartate aminotransferase (AST), alanine aminotransferase (ALT), gamma-glutamyl transferase (GGT), amylase, lipase, alkaline phosphatase (ALP), lactate

dehydrogenase (LDH), bilirubin, calcium, albumin, phosphate, magnesium, uric acid, and glucose. Electrolytes include sodium, potassium, chloride, bicarbonate, blood urea nitrogen (BUN), and serum creatinine. Hematology includes hematocrit, hemoglobin, platelet count, WBC count (total and differential), RBC count, ANC, and flow cytometric analysis of T and B cell counts as well as peripheral blood lymphocyte subsets (CD3, CD4, CD8, CD19, and CD16/56). Urinalysis includes blood, glucose, protein, specific gravity, and microscopic examination (if clinically indicated).

Laboratory assessments for safety will be tested locally.

It is anticipated that some laboratory values may be outside of the normal value range due to the underlying disease or recovery from conditioning. As in routine practice, the Investigators should use their medical judgment when assessing clinical significance. Clinical significance is defined as any worsening in laboratory measurements which has medical relevance and which results in a change in medical care. If any CS laboratory worsening from Baseline is noted, the changes will be documented as AEs in the AE eCRF. The Investigator will also assess the relationship to study treatment (see Section 9.2.1 for guidance on reporting, recording, and assessing AEs) for all CS out of range values. The Investigator will continue to monitor the subject with additional laboratory assessments until (1) values have reached normal range and/or baseline, or (2) in the judgment of the Investigator, out of range values are not related to the administration of study drug or other protocol-specific procedures.

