9.2 Safety Monitoring

Investigators are responsible for monitoring the safety of subjects who have entered this study and for alerting the Sponsor or its designee to any event that seems unusual, even if this event may be considered an unanticipated benefit to the subject.

The Investigator is responsible for the appropriate medical care of subjects during the study.

If an SAE that is considered related to a study procedure or the study causes a subject to discontinue before completing the study, the Investigator remains responsible for following the event through an appropriate health care option. The subject should be followed for 30 days or until the event is resolved, whichever is longer. Frequency of follow-up evaluation is left to the discretion of the Investigator.

The Sponsor's medical representative or designee will monitor safety data throughout the course of the study.

The Sponsor's medical representative or designee will review SAEs within time frames mandated by company procedures. The Sponsor's medical representative or designee will, as appropriate, periodically review the following:

- Trends in safety data
- Laboratory analytes
- AEs, including monitoring of infections and malignancies

If a subject experiences elevated ALT or AST > 3×the upper limit of the normal range or elevated total bilirubin > 2×the upper limit of the normal range, clinical and laboratory monitoring should be initiated by the Investigator. Details for hepatic monitoring depend upon the severity and persistence of observed laboratory test abnormalities. To ensure subject safety and comply with regulatory guidance, the Investigator is to consult with the Sponsor's medical representative or designee regarding collection of specific recommended clinical information and follow-up laboratory tests.

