11.8.3 Adverse Events

Adverse events will be coded using MedDRA. Adverse events will be grouped by System Organ Class and Preferred Term and summarized. The summary tables will present the frequency and percentage of total subjects by System Organ Class and Preferred Term.

For the summaries of AEs, subjects who experience the same AE (in terms of the MedDRA Preferred Term) more than once will be counted only once for that event in the number of subjects; however, all occurrences of the same event will be counted in the number of events.

Adverse event summaries will be restricted to treatment-emergent AEs (TEAEs) only. Treatment-emergent adverse events are defined as AEs that commence on or after the time of first study treatment administration. AEs without an onset date or time will be defined as TEAEs except where an incomplete date (eg, month and year) clearly indicates that the event started prior to start of first study treatment administration or if the AE stop date indicates that the event started and/or stopped prior to start of first study treatment administration.

Incidence of TEAEs as well as duration, severity, relationship to study treatment, outcome, and actions taken will be listed for each subject. In addition, listings of TEAEs leading to discontinuation of the study, SAEs, and deaths will be provided if applicable.

The following TEAE summaries will be provided:

- Overall summary of TEAEs:
 - Any TEAE
 - Any severe / ≥ CTCAE Grade 3 TEAE
 - Any TEAE considered as related to any study treatment (assessed by the Investigator as being possibly related, probably related, or definitely related)
 - Any TEAE leading to discontinuation from the study
 - Any serious TEAE
 - Any life-threatening TEAE
 - Any TEAE leading to death
- TEAEs overall and by System Organ Class and Preferred Term
- TEAEs related to any study treatment overall and by System Organ Class and Preferred Term (a TEAE related to study treatment is defined as any TEAE assessed by the Investigator as being possibly related, probably related, or definitely related to any study treatment)
- TEAEs by severity/CTCAE Grade overall and by System Organ Class and Preferred Term
- TEAEs leading to study discontinuation overall and by System Organ Class and Preferred Term
- Serious TEAEs overall and by System Organ Class and Preferred Term
- TEAEs of interest (related TEAEs, infections, infertility, and malignancies)

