5.7.9. Duration of Adverse Events

Duration of Adverse Events (in DD:HH:MM) will be calculated as:

Duration of Adverse Event = (Resolution Date and Time) – (Onset Date and Time)

Where time is missing, only dates will be used. If a resolution or onset date is missing or incomplete, no duration will be derived.

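### The AE outcome Recovered/Resolved also covers events that have only improved, so listed AE outcomes are unreliable and listed durations may be too short

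*Protocol*

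**What the plan says.** Protocol 9.2.1.4 lists the outcomes an Investigator may assign to an AE, and SAP 10.1.1.7 carries the same definitions. Three matter here:

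- "Recovered/Resolved: the event has improved or the patient recuperated"
- "Recovering/Resolving: the event is improving"
- "Not Recovered/Not Resolved: the event has not improved or the patient has not recuperated"

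SAP 5.7.9 computes duration from the resolution date ("Duration of Adverse Event = (Resolution Date and Time") less the onset date and time, and adds: "If a resolution or onset date is missing or incomplete, no duration will be derived". Protocol 11.8.3 states where these items are reported: "Incidence of TEAEs as well as duration, severity, relationship to study treatment, outcome, and actions taken will be listed for each subject". SAP 10.1.1.8 likewise puts duration and outcome in the AE listing.

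Two follow-up rules depend on resolution. Protocol 9.2 covers a related SAE that makes a subject discontinue: "The subject should be followed for 30 days or until the event is resolved, whichever is longer". Protocol 7.4.1 has a rule of the same form for a subject found ineligible before infusion who had an AE after study procedures.

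Separately, Protocol 9.1.3 continues laboratory monitoring until "values have reached normal range and/or baseline", or until the Investigator judges the values unrelated. Sections 9.1.1 and 9.1.2 use return to baseline, or Investigator judgment, for examination findings and vital signs.

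**The concern.** The word joining the two halves of the Recovered/Resolved definition makes improvement sufficient on its own. A site that follows the text can close as resolved an event the subject still has, and two sites can code the same course differently. Any error toward Resolved flatters the product.

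This matters because safety is a primary objective, an outcome is required for every AE, and the study is small (8 to 16 subjects planned; per SAP 5.1, only switch-stable subjects enrolled). With an abbreviated report, the listings are a main way to read the course of an event. Events that can improve partially are central here. Protocol 9.2.1 makes low counts above set grades AEs regardless of clinical significance, and makes fertility events AEs of special interest. Section 9.1.5 names both azoospermia and oligospermia as reduced fertility, so a move from the first to the second is an improvement to a state that is still abnormal.

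**Working it through.** The plan gives no figure to reproduce. The check sets the definitions side by side and traces where the outcome and the resolution date are used.

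**1. Do the categories exclude one another?** Applying the three definitions literally:

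| State of the AE | Recovered/Resolved | Recovering/Resolving | Not Recovered/Not Resolved |
|---|---|---|---|
| Gone, subject well | fits | no | no |
| Better, still present, still getting better | fits (improved) | fits | fits (not recuperated) |
| Better, still present, now static | fits (improved) | no | fits (not recuperated) |
| No better | no | no | fits |

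The two middle rows fit three and two categories. No definition asks for absence of the event or return to Baseline.

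**2. What could happen to duration?** Let onset be t0, first improvement t1 and true end t2. SAP 5.7.9 intends t2 − t0. If a site enters t1 as the resolution date, the listing shows t1 − t0, which is short by t2 − t1. Assumed dates, to show direction only: onset Day 10, improved Day 20, gone Day 60. The intended duration is 60 − 10 = 50 days and the listed one 20 − 10 = 10 days. If the event never ends on study, the SAP would derive no duration, yet the listing would show 10 days. If t1 = t2, or if the site enters the true end date, there is no error. The documents do not say which date sites enter. The eCRF completion guidelines mentioned in Protocol 9.2.1.2 are not among them.

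**3. Where do outcome and duration go?** Both go to subject listings (Protocol 11.8.3, SAP 10.1.1.8), and no summary table of either is planned. The tables of AE incidence, CTCAE grade, relatedness and onset period do not use the outcome code; only deaths are counted. The end date enters treatment emergence only where the start date is partial or missing (SAP 5.7.15), a corner case I treat as negligible.

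**4. Which follow-up rules depend on resolution?** Only the two in Protocol 7.4.1 and 9.2. Both take the longer of 30 days and resolution, so a premature Resolved code can shorten follow-up only beyond day 30, and only for those subjects.

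**5. Do other rules supply the missing end state?** In part. Sections 9.1.1 to 9.1.3 give a return-to-baseline or normal-range criterion for examination, vital-sign and laboratory monitoring. Section 9.1.5 gives none for reproductive measures and refers to institutional guidelines. Symptom AEs with no measured finding have none either.

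**The case against.** The other side concedes the overlap and contests its consequences. Most of that case stands.

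- **Cytopenia.** A reader might infer that cytopenia durations are understated by a definite amount because a fall from Grade 4 to Grade 3 counts as improved. The documents do not support this. Protocol 9.2.1 makes any Grade 3 or higher platelet count an AE in its own right, so the event cannot simply be closed at that point. SAP 10.1.1.8 expects a single AE to be captured several times as its grade changes, so a short record may be ordinary grade-change entry.
- **Follow-up.** A reader might infer that follow-up generally ends early. It does not. The two rules are narrow and have the 30-day floor, and monitoring under 9.1.1 to 9.1.3 does not use the outcome code. The schedules of assessments ask for every effort to keep following discontinued subjects for safety, and infused subjects who leave may enter the long-term study.
- **Conflict with 9.1.3.** A reader might call this a contradiction. One passage says when to stop monitoring and the other how to label an outcome, so both can be obeyed. They do use different end states and should be reconciled.
- **Independent reporting.** ANC and platelets are listed, flagged and plotted per subject, and reproductive results are listed with change from Baseline. Persistent abnormality stays visible there.
- **Timing.** SAP Section 1 says the study was prematurely discontinued, so a protocol amendment would not change codes already entered.

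What none of this removes is the overlap itself: the outcome column remains unreliable for any AE that improved without ending.

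**Conclusion.** The definitional defect is established by the text of both documents: an AE that is better but still present can properly be coded Recovered/Resolved, so listed outcomes are unreliable. The effect on listed durations is a possibility. It rests on the assumption that sites entered the improvement date as the resolution date, and the documents can neither confirm that nor size it. The reach is the AE listings plus, beyond 30 days, the two follow-up rules. AE incidence, grade and relatedness tables are unaffected, and with no formal tests planned no inference is at stake. This is a modest point, worth correcting because the remedy is cheap and safety is a primary objective.

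**What to change.** In SAP 10.1.1.7, and in Protocol 9.2.1.4 if it is ever amended, make the categories mutually exclusive:

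- **Recovered/Resolved:** the event is no longer present, or is back to the normal range or the subject's Baseline status, reconciled with Protocol 9.1.1 to 9.1.3.
- **Recovering/Resolving:** improved but not yet there.
- **Not Recovered/Not Resolved:** no improvement.

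State in SAP 5.7.9 that the resolution date is the date this definition of Recovered/Resolved is met. Before lock, query every AE coded Resolved whose last laboratory or reproductive result is still worse than Baseline. Link the entries of AEs recorded several times because of grade changes first, so that a grade-change end date is not mistaken for a false resolution.

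SAP Section 1 allows amendments before lock, so the SAP text and the query are the workable parts. A protocol change needs formal amendment and ethics approval and would not recode existing data. The cost is a few lines of SAP text and a small query. Some listed outcomes and durations will become less favourable. The query cannot reach symptom AEs with no measured result, so their listed outcomes should be read with that caution.

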9.2.1.5 Serious Adverse Events

The SAE collection begins after the subject has signed informed consent. Elective or planned procedures and/or hospitalizations that were scheduled or anticipated prior to entry into the study should not be reported as SAEs. During the study, elective, anticipated, or planned procedures/hospitalizations should not be reported as SAEs unless the underlying medical condition has worsened over the course of the study. For SAEs that are due to worsening underlying medical conditions, the SAE form should be marked as "due to underlying medical condition."

Study site personnel must alert the Sponsor or its designee of any SAE within 24 hours of Investigator awareness of the event via a Sponsor-approved method. This 24-hour notification requirement refers to the initial SAE information.

An SAE is any AE from this study that results in 1 or more of the following outcomes:

- Results in death
- Requires or prolongs hospitalization
- Is life-threatening (that is, immediate risk of dying)
- Persistent or significant disability/incapacity
- Congenital anomaly or birth defect
- Other medically important serious event

Important medical events that may not result in death, be life-threatening, or require hospitalization may be considered SAEs when, based upon appropriate medical judgment, it may jeopardize the subject and may require medical or surgical intervention to prevent one of the outcomes listed in this definition.

The SAEs occurring up to and including the subject's last study visit will be collected regardless of the Investigator's opinion of causation.

If an Investigator becomes aware of SAEs occurring to a subject after the subject's participation in the study has ended (including any protocol-required post-treatment follow-up), the Investigator should report the SAEs to the Sponsor regardless of the Investigator's opinion of causation.

Information on SAEs expected in the study population independent of study treatment and that will be assessed by the Sponsor in aggregate periodically during the course of the study may be found in the Reference Safety Information section of the Investigator's Brochure.

9.2.1.6 Suspected Unexpected Serious Adverse Reactions

Suspected unexpected serious adverse reactions (SUSARs) are serious events that are not listed in the Investigator's Brochure and that are identified as related to study treatment. United States 21 Code of Federal Regulations (CFR) 312.32 and European Union Clinical Trial Directive 2001/20/EC and the associated detailed guidances or national regulatory requirements in participating countries require the reporting of SUSARs. The Sponsor has procedures that will be followed for the recording and expedited reporting of SUSARs that are consistent with global regulations and the associated detailed guidances.

9.2.1.7 Reporting Adverse Events

All non-serious AEs must be recorded in the eCRF upon awareness.

All SAEs must be reported to the to Sponsor or designee, via the SAE contact in the Safety Management Plan, within 24 hours of the Investigator or their staff becoming aware of them. The Investigator must complete, sign, and date the SAE pages, verify the accuracy of the information recorded on the SAE pages with the corresponding source documents, and send a copy via electronic submission to the safety database or e-mail. Facsimile transmission may be used in the event of electronic submission or e-mail failure.

When further information becomes available, the SAE Report Form should be updated with the new information and reported immediately via the same methods as the initial information.

Additional follow-up information, if required or available, should be reported to the Sponsor or designee within 24 hours of the Investigator or their staff becoming aware of this additional information via same manner as above.

Follow-up information should be recorded on a follow-up SAE Report Form and placed with the original SAE information and kept with the appropriate section of the SAE Report Form and/or study file.

These timelines for reporting information to the Sponsor must be followed for all initial SAE reports and for all follow-up versions of the initial reports.

All SAEs (related and unrelated) will be recorded from the signing of informed consent until the Week 52 (or Early Termination) Visit.

For all SAEs the Investigator must provide the following:

- Appropriate and requested follow-up information in the time frame detailed above
- Causality of the SAE(s)
- Outcome of the SAE(s)
- Redacted medical records and laboratory/diagnostic information

9.2.1.8 Sponsor Reporting Requirements

The Sponsor or its legal representative is responsible for notifying the relevant regulatory authorities of SAEs meeting the reporting criteria. This protocol will use the current Investigator's Brochure as the Reference Safety Document. The expectedness and reporting criteria of an SAE will be determined by the Sponsor from the Reference Safety Document.

9.2.1.9 Investigator Reporting Requirements

The Investigator must fulfill all local regulatory obligations required for the study Investigators. It is the PI's responsibility to notify the IRB/IEC of all SAEs that occur at his or her site. Investigators will also be notified of all SUSAR events that occur during the clinical study. Each site is responsible for notifying its IRB/IEC of these additional SAEs according to local requirements.

9.2.2 Exposure During Pregnancy and/or Lactation

Pregnancy data will be collected during this study for all subjects.

Pregnancy is permissible during the study provided that the gestational carrier is not a subject in the study and the pregnancy is the result of either:

- a. A fertilization involving the subject's gametes that occurred before the subject's busulfan exposure, or
- b. A fertilization that involves gametes collected from the subject before busulfan exposure, or
- c. A fertilization using donor sperm or egg in lieu of the subject's gametes.

Exposure during pregnancy must be recorded and the subject followed until the outcome of the pregnancy is known (spontaneous miscarriage, therapeutic abortion, elective termination, normal birth, congenital abnormality, or ongoing), even if the subject discontinues from the study.

If a female subject or a male subject's partner becomes pregnant while treated or exposed to study treatment, the Investigator must submit a pregnancy form to the Sponsor or designee via the same method as SAE reporting (see Section 9.2.1.7). When the outcome of the pregnancy becomes known (ie, spontaneous miscarriage, elective termination, normal birth, or congenital abnormality), the pregnancy form must be completed and returned to the Sponsor or designee. If additional follow-up is required, the Investigator will be requested to provide the information.

For any partner pregnancies reported during the study, the pregnancy must be followed until the outcome of the pregnancy is known, even if the subject discontinues from the study.

Pregnancy in itself is not regarded as an AE unless there is a suspicion that study treatment may have interfered with the effectiveness of a contraceptive medication. However, complications of pregnancy and abnormal outcomes of pregnancy are AEs, and many may meet criteria for an SAE (such as ectopic pregnancy, spontaneous abortion, intrauterine fetal demise, neonatal death, or congenital anomaly). Elective abortions without complications should not be reported as AEs.

9.3 Engraftment and Efficacy Measures

9.3.1 Vector Copy Number

Blood samples for measurement of average VCN in PBLs and bone marrow aspirate by qPCR and/or ddPCR analysis will be collected at times shown in Table 4, Table 5, and Table 6. Samples will be tested at a central laboratory.

